5.6.2 Evaluation of Progression in non-irradiated Lesions

Progressive Disease: The appearance of one or more new lesion(s) and/or unequivocal progression of existing non-irradiated lesions. If there is any question regarding whether a non-irradiated lesion meets the criteria for progression, please check with the study PI, [name].

6.0 Adverse Experiences

6.1 Definitions

6.1.1 Adverse Events (AE)

An AE is any untoward medical occurrence in a patient or clinical investigation subject administered a pharmaceutical product and which does not necessarily have a causal relationship with this treatment. An adverse experience or event (AE) can therefore be any unfavorable and unintended sign (including an abnormal laboratory finding), symptom, or disease temporally associated with the use of a medicinal (investigational) product, whether or not related to the medicinal (investigational) product.

Hospitalization for elective surgery or routine clinical procedures that are not the result of an AE (e.g., surgical insertion of central line) need not be considered AEs and should not be recorded as an AE. Disease progression should not be recorded as an AE, unless it is attributable by the investigator to the study therapy.

The NCI's Common Terminology Criteria for Adverse Events (CTCAE), Version 3.0 will be used to identify the type and to grade the severity of unanticipated adverse events in patients participating on this study.

6.1.2 Unexpected AE

An unexpected adverse event is considered unexpected if the specificity or severity of which is not consistent with the risk information described in the general investigational plan.

For this study, machine malfunction that affects delivery of treatment as defined as the inability to complete a fractional dose will be recorded and reported as unexpected.

6.1.3 Serious AE

An AE is considered serious if in the view of the investigator or sponsor, it in any of the following outcomes:

- Death

- A life-threatening (places the subject at immediate risk of death from the event as it occurred);
- Requires inpatient hospitalization (>24 hours) or prolongation of existing hospitalization*
- Results in a persistent or significant disability/incapacity
- Results in a congenital anomaly/birth defect
- Important medical events that may not result in death, be life-threatening, or require hospitalization may be considered a serious adverse drug experience when, based upon appropriate medical judgment, they may jeopardize the patient or subject and may require medical or surgical intervention to prevent one of the outcomes listed in the definition.

*Hospitalization for anticipated or protocol specified procedures such as administration of chemotherapy, central line insertion, metastasis interventional therapy, resection of primary tumor, or elective surgery, will not be considered serious adverse events.

6.2 Documentation of non-serious AEs

For non-serious AEs or SAEs, documentation must begin from day 1 of study treatment and continue through the 30 day follow-up period after treatment is discontinued.

For all adverse events reported or observed, the information should be recorded in the electronic Case Report Forms (eCRFs) for that patient. Please include a full description of the event, its severity or toxicity grade, the relationship to the study drug, and the treatment, outcome and sequelae of the event. Documentation should occur at least monthly.

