3.3 Expected Toxicities

There are a few specific toxicities that are of concern in the irradiation of tumors in the liver. The first concerns the overall maintenance of good hepatic function. From the data in the literature^{4,5}, this appears to be strongly related to the amount of liver in the radiation field treated to moderate dose. The data from liver resection surgery has shown that with a proliferative response, the liver can regenerate itself after removal of ½ or more of the liver. This regeneration will likely not occur if the remaining liver has received a significant amount of radiation, although the dose that would prevent regeneration is not known.

Secondly, the primary biliary radicals could be damaged by the radiation. This would likely be a late response, although initial edema could produce an acute temporary obstruction that would likely be minimized by the use of steroids. Long term, fibrosis could occur producing biliary obstruction.

Third, there can be vascular injury producing a veno-occlusive picture with hepatomegaly and other signs of liver failure that can occur about 3 months after irradiation. In addition, as the liver is in close proximity to multiple normal structures, the tolerance of these structures (liver, lung, esophagus, duodenum) must also be considered as ulceration and necrosis could occur if those structures are irradiated to high dose. Toxicity from structures distant to the radiation beam is very unlikely. Doses to all the above mentioned normal tissues can be calculated during the planning phase of the therapy to allow us to estimate high-risk sites.

These toxicities described above are primarily captured in the CTCAE, Version 3.0 formulation as hepatic and biliary tract related, and they will be measured accordingly. We would not expect toxicities in other organs other than liver, stomach, bowel, or lung. However, all toxicities that are not clearly ascribable to other unrelated causes or to tumor progression will count for the toxicity evaluation.

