5.4 Post-treatment Assessments (Up to week 20 after RT Treatment)

- History and physical examination
- Performance status
- Laboratory studies including CBC, and liver function tests
- CT, PET or MRI of the liver will be performed at, 8 and 20 weeks after the completion of radiation therapy and then at regular intervals per Section 5.1.
- Toxicity assessment (NOTE: this should occur up to week 20 regardless of whether disease recurs prior to this point or not).

5.5 Follow-up Assessments:

Follow-up will be done every three months for two years, or until disease progresses in an irradiated liver lesion. If disease progresses in a non-irradiated lesion only, follow-up will continue until disease progresses in one of the irradiated liver lesions. Once disease progresses in an irradiated liver lesion, protocol follow-up will cease other than follow-up of any unresolved treatment-related toxicity. Follow-up assessments will include:

- History and physical examination
- Performance status
- Laboratory studies for liver function tests
- CT, PET or MRI of the liver.
- Toxicity assessment

Patients in whom high dose irradiation is delivered to the main hepatic ducts or common bile duct will be considered for elective stent placement within the first 4 weeks after completion of radiation therapy to prevent biliary obstruction.

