6.3 SAEs

6.3.1 Timing

After informed consent but prior to initiation of study medications, only SAEs caused by a protocol-mandated intervention will be collected (e.g. SAEs related to invasive procedures such as biopsies, medication washout, or no treatment run-in).

For any other experience or condition that meets the definition of an SAE recording of the event must begin from day 1 of study treatment and continue through the 30 day follow-up period after treatment is discontinued.

Documentation and Notification

These events must be recorded in the SAE console within Oncore™ for that patient within 24 hours of learning of its occurrence. For Affiliate sites, an email must also be sent to the NCCN Study Coordinator indicating that an SAE has been entered into Oncore (email contact will be provided at study start-up).

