7.0 DATA MANAGEMENT AND STATISTICAL ANALYSIS

7.1 Study Design

The primary end-point of this study will be hepatic tolerance to the radiation treatment. This will be complicated by patients who could have progressive disease in the liver that could result in worsening liver function studies. Damage secondary to radiation therapy should appear within 3 months, so that will be the primary time for evaluation. Liver tolerance will be determined by the following:

1). The primary end-point will be the development of radiation induced liver disease as measured by the > 2-fold worsening of liver functional parameters, clinically apparent worsening of portal hypertension, new or worsening bleeding esophageal varices, or worsening ascites within the first 3 months from initiation of treatment. These will be considered dose-limiting hepatic toxicities. Increase in hepatic enzymes by less than 2-fold alone will not be considered a dose-limiting radiation induced toxicity if they are not accompanied by other signs of deteriorating liver function as any irradiation of normal liver would be expected to elevate enzymes.. The two patient cohorts will be evaluated separately for determination of toxicity. Deteriorating liver function that can be explained by tumor progression or other non-treatment related events will not be considered a treatment toxicity for the purpose of this analysis.

A dose level will be considered beyond tolerance depending on the fraction of patients who experience a dose-limiting radiation induced hepatic toxicity. See Table 3. Once this happens, enrollment to that dose level will be halted. If this happens at dose level 1, subsequent patients eligible for full dose therapy will enroll into dose level -1. If dose level -1 is found intolerable in patients eligible for full dose therapy, the trial will be stopped.

Patients will also be evaluated for other unexpected toxicities according to the NCI CTCAE, Version 3.0.. Unexpected Grade 3 toxicities thought to be due to therapy will be scored as 1 and unexpected Grade 4 toxicities thought to be due to therapy will be scored as 2. A patient with both unexpected Grade 3 and Grade 4 toxicities will be counted as a patient with unexpected Grade 4 toxicity. If the total score exceeds 3 in the first 3, 4, or 5 patients, or exceeds 4 at any point within a dose level, enrollment to that dose-level will be halted and that dose will be considered beyond tolerance. See Table 4.

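### AE documentation and 24-hour SAE entry end 30 days after treatment, leaving roughly half of the 3-month DLT window outside expedited reporting

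*Combined protocol and SAP*

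**What the plan says.** **Recording window.** For non-serious AEs and SAEs, Section 6.2 states that "documentation must begin from day 1 of study treatment and continue through the 30 day follow-up period after treatment is discontinued". Section 6.3.1 repeats the limit for SAEs: "recording of the event must begin from day 1 of study treatment and continue through the 30 day follow-up period after treatment is discontinued". The notification paragraph that follows refers to these same events and requires entry in the OnCore SAE console "for that patient within 24 hours of learning of its occurrence".

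**Endpoint window.** Sections 3.2 and 7.1 define the DLT as radiation-induced liver disease, whose listed signs end with "worsening ascites within the first 3 months from initiation of treatment". Section 7.1 gives the reason: "Damage secondary to radiation therapy should appear within 3 months, so that will be the primary time for evaluation". Section 3.3 describes a veno-occlusive picture with "other signs of liver failure that can occur about 3 months after irradiation" and calls biliary damage a likely late response.

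**Assessment schedule.** Section 5.1 lists toxicity assessment during treatment, at post-treatment Weeks 1, 4, 8 and 20, and then every 3 months for two years. Section 5.4 adds that "this should occur up to week 20 regardless of whether disease recurs prior to this point or not".

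**Decisions that use the events.** Tables 3 and 4 are running stopping rules that apply from the third patient at a dose level. Any Grade 5 toxicity thought related to therapy suspends the trial for evaluation. Tables 5A and 5B govern escalation.

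**The concern.** Section 6 closes its recording and notification duties well before the window in which the primary endpoint is counted, and before the time at which Section 3.3 says one form of liver injury can occur. After the 30-day limit, a site following Section 6 has no stated duty to enter within 24 hours a variceal bleed, an admission for liver failure or a treatment-related death on day 60, for example.

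What is at stake is timeliness. The stopping rules in Tables 3 and 4 and the Grade 5 suspension protect the next patients only if the study team hears of an event soon after it happens. If a late hepatic event is first learned of at a scheduled visit, patients may meanwhile be entered at a dose level whose stopping condition has already been met.

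There is also a question of which record counts. Section 6 does not refer to the longer toxicity schedule in Section 5. Section 5 does not say whether its toxicity findings are entered as AEs or SAEs. Table 4 events (unexpected Grade 3 and 4 toxicities) have no time window of their own in Section 3.2 or 7.1, so a site could take the Section 6 limit as the cut-off for them.

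**Working it through.** The plan gives no figure of its own to reproduce. The check compares the windows.

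**Inputs**
- *T*, the day of the last fraction, with treatment starting on day 1. Section 3.2 gives a general range of 3 to 15 days. For the first cohort it also sets a minimum of 5 days and completion within 2 weeks, and a Section 5.1 footnote repeats both limits without restriction to a cohort. I use 5 to 15.
- Recording ends 30 days after treatment (Sections 6.2 and 6.3.1).
- *W*, the DLT window: 3 months from initiation (Sections 3.2 and 7.1). The protocol does not convert this to days. I assume 90, 91.3 or 92 days, with 84 days (12 weeks) as a sensitivity check.

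**Step 1: last day of recording** = T + 30
- T = 5: 5 + 30 = day 35
- T = 15: 15 + 30 = day 45

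**Step 2: share of the DLT window outside recording** = (W − (T + 30)) / W

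| W (days) | T = 5 | T = 15 |
|---|---|---|
| 84 | (84 − 35)/84 = 58.3% | (84 − 45)/84 = 46.4% |
| 90 | (90 − 35)/90 = 61.1% | (90 − 45)/90 = 50.0% |
| 91.3 | (91.3 − 35)/91.3 = 61.7% | (91.3 − 45)/91.3 = 50.7% |
| 92 | (92 − 35)/92 = 62.0% | (92 − 45)/92 = 51.1% |

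The range is about 46% to 62%. A 3-day course, which the 5-day minimum rules out, would give (92 − 33)/92 = 64.1% at most.

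**Step 3: where the scheduled visits fall** = T + 7 × week
- Week 4: 5 + 28 = day 33 to 15 + 28 = day 43, just inside the recording window
- Week 8: 5 + 56 = day 61 to 15 + 56 = day 71, inside the DLT window but after recording has closed
- Week 20: 5 + 140 = day 145 to 15 + 140 = day 155, well after the DLT window

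**Step 4: part of the DLT window after the Week 8 visit** (W = 91.3)
- T = 5: 91.3 − 61 = 30.3 days
- T = 15: 91.3 − 71 = 20.3 days

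No scheduled visit falls in these last 20 to 30 days (13 to 23 days if W = 84). Reporting triggered by the event itself is the prompt route there, and Section 6 has ended it.

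**Step 5: effect of recording through Week 20** (W = 91.3)
- 145 − 91.3 = 53.7 days to 155 − 91.3 = 63.7 days beyond the end of the DLT window. The uncovered share becomes zero.

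**The case against.** The strongest reply is that DLT capture does not rest on Section 6. The endpoint and its 3-month window are set in Sections 3.2 and 7.1. Section 5.1 schedules toxicity assessment and liver function tests at Weeks 4, 8 and 20. Section 3.3 counts all toxicities not clearly due to unrelated causes or progression. Nothing says that Tables 3 to 5B draw only on Section 6 records. Section 3.2 also requires 3 months of toxicity follow-up for all patients in a cohort before escalation. All of this stands, and it rules out four stronger inferences that a reader might draw:

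- *That no AEs are recorded after the 30-day limit.* Toxicity assessment continues. Section 6.2 also says that all AEs reported or observed go on the eCRF, in a sentence with no time limit of its own. That sentence follows the 30-day limit without clearly overriding it, so the text is ambiguous rather than silent.
- *That DLT counts will be too low, or that escalation could rest on 30-day data.* The separate 3-month evaluation stands in the way. A wrong Table 5A decision would need a DLT to be missed there too.
- *That the uncovered days are the period of peak risk.* Section 3.3 says only that the injury can occur at about 3 months.
- *That more than half of the window is always uncovered.* For a 15-day course the share is exactly 50.0% at 90 days and 46.4% at 84 days.

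Other routes for late events exist but are partial. The Grade 5 rule has no time limit, yet it states no notification step. Prompt IRB reporting under Sections 6.3.2 and 8.6.3 covers only events that qualify as Unanticipated Problems. The teleconferences in Section 6.4 are bi-weekly only if accrual warrants, and they can discuss only what sites have passed on.

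Finally, a longer reporting window adds no visit or laboratory test at month 3. It would not detect a change in liver function that only a test would show. That limitation is correct.

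**Conclusion.** The mismatch is real, and its main consequence is late notice. Section 6 is not reconciled with Sections 3.2, 5.4 and 7.1. AE documentation and 24-hour SAE entry end on about day 35 to 45, while the DLT window runs for 3 months from initiation and toxicity assessment is required to Week 20. Roughly half of the DLT window lies outside expedited reporting.

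This rests on a 5- to 15-day course, on 3 months counted as 84 to 92 days, and on reading the 24-hour rule as applying to the SAEs whose recording Section 6.3.1 limits. The percentage is a share of calendar days. It does not estimate how many events would be missed, and the documents give no basis for such an estimate.

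The supported consequence is that a serious hepatic event or related death between visits could become known late. The Table 3 and 4 stopping rules and the Grade 5 suspension would then act late while accrual continues at that dose level. The documents do not show that DLTs would go uncounted.

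**What to change.** In Sections 6.2 and 6.3.1, replace the 30-day limit so that AE documentation and 24-hour SAE entry run at least to the end of the 3-month DLT window. Running both through the Week 20 assessment is preferable, because Section 5.4 already requires that visit and one end date would then serve both sections.

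Add one sentence to Section 6 stating that toxicity findings from Section 5 visits are recorded as AEs or SAEs and feed Tables 3, 4, 5A and 5B and the Grade 5 rule.

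Recording related Grade 3 or higher events after Week 20 is optional and is not needed to correct the mismatch.

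The cost is protocol wording and eCRF instructions, with no new visits. The downside is more SAE entries from disease-related hospitalisations.

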3.2. Treatment Dosage and Administration

Fiducial placement:

Standard techniques will be used as for biopsy, but gold seed markers compliant with the CyberKnife software will be placed in the vicinity (within 6 cm) of the tumor. At least 3, but generally 4-5, markers will be placed in such a manner as to not be co-linear, and as widely spaced as possible. Markers can be placed within the tumor mass, but some of the markers should be placed in the normal liver surrounding the tumor. It is recommended that at least 1 gold fiducial should be implanted inside the gross tumor. The fiducials may be placed via percutaneous needle placement under imaged guidance and local anesthesia or utilizing endoscopic ultrasound techniques in the standard fashion. Similar to fine needle biopsy, it is possible that placement of the fiducials may result in inflammation, bleeding, infection, pneumothorax or bile leak.

Immobilization Cradle and Treatment Planning CT Imaging

At least 6 days after fiducial placement (to enable resolution of any injury that may have occurred during fiducial placement and to allow for fiducial stabilization), subjects will return to the Radiation Oncology Clinic. If fiducials have been placed surgically, then the planning CT should be done as soon after 6 days as deemed clinically appropriate.

Prior to or at this visit, a radiation therapy immobilization device (i.e. Alpha Cradle) will be custom made for each subject to position them during the treatment.

While positioned in the immobilization device, a treatment planning CT scan with and without IV contrast will be taken. Patients with allergies to the contrast agent will be premedicated per institutional protocol. The CT scans taken for treatment planning will be taken with a breath hold with the tumor located approximately midway axially of the slices required. This imaging set will be downloaded to the CyberKnife treatment planning system to develop the radiosurgery treatment plan.

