5.2 Pre-study Assessments

- Informed Consent
- History and physical examination
- Performance status
- Chest x-ray
- Laboratory studies including: CBC, LFT, Serum creatinine
- CT and/or MRI of the liver; PET scan is optional
- Pregnancy test within 14 days pre-study, and only if clinically appropriate

Fiducial placement: Prior to CT planning gold seed markers compliant with the CyberKnife software will be placed in the vicinity (within 6 cm) of the tumor as described in Section 3.2. CT planning in Radiation Oncology to be done at least 6 days after fiducial placement.

Liver biopsy: Tumor biopsies should occur pre-study (within 14 days of study entry), although earlier biopsies can be acceptable with the approval of the Principle Investigator (PI) if sufficient diagnostic information has been obtained. Tumor biopsies will be performed by qualified radiology/interventional radiology personnel under CT or US guidance (presumably at the time of fiducial placement) of the tumor site deemed least likely to produce patient discomfort or complications. Patients should be monitored per the site standard of care after the procedure and any complications graded and reported utilizing the criteria for toxicity reporting described in section 6. Up to three passes should be made if safe in the judgment of the physician performing the procedure. A 14-20 FG needle will be used, at the discretion of the interventional radiologist.

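### Non-serious complications of the required fiducial placement, or of an on-study biopsy, need not be recorded before day 1 of treatment; for biopsy this conflicts with Section 5.2

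*Combined protocol and SAP*

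**What the plan says.** - **The procedure.** Section 3.1 places the fiducials after consent. Footnote d of the Section 5.1 table puts them after study entry and before radiation. Section 3.2 warns that "placement of the fiducials may result in inflammation, bleeding, infection, pneumothorax or bile leak", and delays the planning CT partly so that any injury can resolve.
- **Start of recording.** Section 6.2: "documentation must begin from day 1 of study treatment".
- **Before treatment.** Section 6.3.1: between consent and the start of treatment, "only SAEs caused by a protocol-mandated intervention will be collected (e.g. SAEs related to invasive procedures such as biopsies" being the example given.
- **Biopsy.** The liver biopsy paragraph of Section 5.2 wants "any complications graded and reported utilizing the criteria for toxicity reporting described in section 6". It expects the biopsy to be done "presumably at the time of fiducial placement". The fiducial paragraph of the same section has no reporting instruction.
- **Counting.** Section 3.3 brings into the toxicity evaluation "all toxicities that are not clearly ascribable to other unrelated causes" or to tumor progression. Section 3.2 excludes hepatic decline explained by non-treatment events, and scores an unexpected Grade 3 or 4 event only if it is thought due to therapy.

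**The concern.** The protocol foresees injury from a procedure that it requires, and allows time for that injury to heal, but asks for a record only if the injury is serious. Two things are at stake. First, the complication rate of fiducial placement is part of what a patient accepts by joining the study, and it could be reported only for serious events. Second, a complication still present when radiation starts would have no required record of when it began or how severe it was beforehand. Section 3.3 counts toxicity unless another cause is clear, so that missing history is the evidence an investigator would need to assign the event to the procedure. It is also unsettled whether a protocol-required procedure is an unrelated cause at all, since fiducial placement is described within the treatment section.

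**Working it through.** The plan states no figure on this point, so the check is a comparison of passages plus the length of the window.

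**1. When is day 1?** Section 6.2 speaks of study treatment and Section 6.3.1 of study medications; neither is defined. Two things point to the start of radiation. The first toxicity assessment marked in the Section 5.1 table is at CyberKnife delivery. Section 6.3.1 also gives biopsy as an example of what comes before treatment starts, and Section 5.2 presumes biopsy and fiducial placement share a session. Column alignment in the table should be checked against the PDF, so the blank pre-study cell for toxicity is supporting evidence only.

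**2. What must be recorded before day 1?**

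| Event before day 1 | Sections 6.2 and 6.3.1 | Section 5.2 |
|---|---|---|
| Serious, from fiducials or biopsy | Collected | Biopsy: grade and report |
| Non-serious, from on-study biopsy | Not required | Grade and report: conflict |
| Non-serious, from fiducials alone | Not required | Silent: gap |

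**3. Length of the window.** Inputs: at least 6 days from fiducials to planning CT (Sections 3.2, 5.1 and 5.2), and radiation generally within 1 to 2 weeks of that CT (Section 3.2). The second figure is an upper limit.
- Minimum: 6 days plus whatever the CT-to-radiation interval turns out to be.
- With the CT on day 6: up to about 6 + 7 = 13 to 6 + 14 = 20 days.
- A later CT lengthens it. If fiducial placement falls under the 8-week pre-study limit in footnote a, the outer bound is 8 × 7 = 56 days.

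**4. Reach into the escalation rules.**
- Tables 4 and 5B count only unexpected events thought due to therapy. Section 6.1.2 defines unexpected by whether an event's specificity or severity departs from the risk information in the plan, and Section 3.2 names the main fiducial risks. Most such events are therefore expected and outside both tables.
- At 5 to 8 patients, Table 5B allows one patient with an unexpected Grade 3 event and none with Grade 4. At 9 or 10 it allows two with Grade 3 and none with Grade 4, or one with Grade 4 and none with Grade 3. One misattributed Grade 3 event alone blocks nothing; it matters only when the level is already at its limit.
- A Grade 4 complication would ordinarily be serious under Section 6.1.3, and so already collected.

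**5. Illustrative rates.** The documents give no complication rate. At an assumed rate r, the expected number among the 40 evaluable patients of Section 7.2 is 40r, and the chance of at least one in a 10-patient level is 1 − (1 − r)^10.

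| Assumed r | 40r | 1 − (1 − r)^10 |
|---|---|---|
| 3% | 1.2 | 26% |
| 5% | 2 | 40% |
| 10% | 4 | 65% |

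These figures describe any complication, serious or not, resolved or not. They do not measure misattribution.

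**The case against.** The strongest defence is that the text does not forbid earlier entries. Section 6.2 fixes when recording becomes mandatory, and its next paragraph sends every event reported or observed to the eCRF. The restriction in Section 6.3.1 stands under the heading for serious events and may limit only those. The specific biopsy instruction in Section 5.2 can be read as adding to the general start date. The complication rate of fiducial placement is not a study objective.

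This shows that a careful site might record the events. It does not show that the protocol requires it: the eCRF sentence follows the day-1 limit without lifting it, and a fiducial-only complication has no instruction in Section 5.2.

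The defence does succeed against several stronger inferences a reader might draw:

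- *Procedure and radiation effects cannot be separated.* An event that resolves before day 1 is not counted as radiation toxicity. One that persists can be seen at the history, examination and toxicity assessment at radiation delivery (Sections 5.1 and 5.3) and judged under the attribution rules.
- *Every Grade 3 event without a hospital stay over 24 hours is lost.* The important-medical-event clause in Section 6.1.3 would make some of these serious, and so collected.
- *Section 5.2 contradicts Section 6 for fiducials as such.* The instruction concerns biopsy, and reaches fiducials only through the presumed shared session.
- *One event can readily overturn an escalation decision.* That needs an event that is unexpectedly severe or wrongly classed, and attributed to therapy, at a level already at its limit.

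**Conclusion.** The point holds as a gap in required safety recording, with a direct conflict between sections for on-study biopsy. Its measurable size is the window: at least 6 days plus the CT-to-radiation interval, so up to about 13 to 20 days when the CT is on day 6. It rests on reading day 1 as the first day of radiation, which the protocol implies but does not define.

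The consequences are an incomplete complication rate for a required invasive procedure, and weaker evidence on onset and grade for events that carry over into radiation. Attribution is harder, not impossible, and the effect on Tables 4 and 5B is small. The 26% to 65% figures should not be cited as the size of the harm: they rest on assumed rates for any complication, whereas the harm needs a non-serious event that persists and is misattributed. The change is still worth making, because it is cheap and supplies the pre-radiation baseline that the counting rule in Section 3.3 relies on.

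**What to change.** 1. In Sections 6.2 and 6.3.1, start documentation of all adverse events related to protocol-required procedures at fiducial placement, and at biopsy when done on study, so that Section 6 agrees with Section 5.2. Define day 1 as the first radiation fraction, if that is what is meant.
2. In the Section 5.1 table, mark a toxicity assessment at the existing planning-CT visit and another immediately before the first fraction.
3. Record onset date and attribution, and list procedure complications separately from radiation toxicity. State whether the fiducial risks named in Section 3.2 count as expected for Tables 4 and 5B, since Section 3.3 does not list them.

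The cost is a few sentences, the added table marks, one separate listing and a few more entries per patient. No new visit or procedure is needed.
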